9.2.3 Reporting Serious Adverse Events After the Protocol-required Reporting Period

There is no requirement to monitor study subjects for serious adverse events following the protocol-required reporting period or after end of study. However, these serious adverse events can be reported to Amgen. If serious adverse events are reported, the investigator is to report them to Amgen within 24 hours following the investigator's knowledge of the event. Serious adverse events reported outside of the protocol-required reporting period will be captured within the safety database as clinical trial cases for the purposes of expedited reporting.

9.3 Adverse Event Adjudication

In order to carefully evaluate cardiovascular and cerebrovascular events during the trial, all adverse events that are deemed to be of potential cardiovascular or cerebrovascular etiology will be submitted to an independent committee for adjudication. Detailed definitions of these events to be adjudicated, including mapping of pre-defined preferred terms potentially indicative of cardiovascular or cerebrovascular etiology, will be provided separately. Adjudication of these adverse events will be based on clinical,

laboratory, and/or imaging data ordered at the treating physician's discretion to assess and treat the event.

The Event Adjudication Committee will be comprised of a group of experienced clinicians with expertise in cardiology and neurology. The Event Adjudication Committee will be responsible for the review and adjudication of the selected adverse events in a blinded manner.

9.4 Pregnancy and Lactation Reporting

If a **female subject becomes pregnant**, or a **male subject fathers a child**, while the subject is taking investigational product/**product-required therapies**, report the pregnancy to Amgen **Global Patient Safety** as specified below.

In addition to reporting any pregnancies occurring during the study, investigators should **report** pregnancies that occur through 16 weeks after the last dose of investigational product/**protocol-required therapies**.

The pregnancy should be reported to Amgen **Global Patient Safety** within 24 hours of the investigator's knowledge of the event of a pregnancy. Report a pregnancy on the Pregnancy Notification Worksheet ([Appendix C](#)). **Amgen Global Patient Safety will follow-up with the investigator regarding additional information that may be requested.**

If a female subject becomes pregnant during the study, the investigator should attempt to obtain information regarding the birth outcome and health of the infant.

If the outcome of the pregnancy meets a criterion for immediate classification as a serious adverse event (eg, female subject experiences a spontaneous abortion, stillbirth, or neonatal death or there is a fetal or neonatal congenital anomaly) the investigator will report the event as a serious adverse event.

If a female breastfeeds while taking investigational product/protocol-required therapies report the lactation case to Amgen as specified below.

Any lactation case should be reported to Amgen **Global Patient Safety** within 24 hours of the investigator's knowledge of event. Report a lactation case on the Lactation Notification Worksheet ([Appendix D](#)). **Amgen Global Patient Safety will follow-up with the investigator regarding additional information that may be requested.**

In addition to reporting a lactation case during the study, investigators should monitor for lactation cases that occur 16 weeks after the last dose of investigational product/protocol-required therapies.

If a male subject's female partner becomes pregnant, the investigator should discuss obtaining information regarding the birth outcome and health of the infant from the pregnant partner.

10. STATISTICAL CONSIDERATIONS

10.1 Study Endpoints, Analysis Sets, and Covariates

10.1.1 Study Endpoints

10.1.1.1 Primary Endpoint

Change from baseline in mean monthly migraine days. The mean monthly migraine days will be calculated using the monthly migraine days from each of the last three months (months 4, 5, and 6) of the double-blind treatment phase.

10.1.1.2 Secondary Endpoints

Efficacy:

- Achievement of at least a 50% reduction from baseline in mean monthly migraine days over the last three months (months 4, 5, and 6) of the double-blind treatment phase
- Change from baseline in mean monthly acute migraine-specific medication treatment days over the last three months (months 4, 5, and 6) of the double-blind treatment phase

Safety:

- Adverse events
- Clinical laboratory values and vital signs
- Anti-AMG 334 antibodies

10.1.1.3 Exploratory Endpoints

- Change from baseline in mean headache impact scores as measured by the Headache Impact Test (HIT-6) over the last three months (months 4, 5, and 6) of the double-blind treatment phase
- Change from baseline in monthly migraine days at assessment timepoints
- Change from baseline in mean monthly migraine attacks over the last three months (months 4, 5, and 6) of the double-blind treatment phase
- Change from baseline in monthly migraine attacks at assessment timepoints
- Change from baseline in mean monthly headache (migraine and non-migraine headache) days over the last three months (months 4, 5, and 6) of the double-blind treatment phase

- Change from baseline in monthly headache (migraine and non-migraine headache) days at assessment timepoints
- Achievement of at least 50% reduction from baseline in monthly migraine days at assessment timepoints
- Achievement of at least 75% reduction from baseline in mean monthly migraine days over the last three months (months 4, 5, and 6) of the double-blind treatment phase
- Achievement of at least 75% reduction from baseline in monthly migraine days at assessment timepoints
- Achievement of 100% reduction from baseline in mean monthly migraine days over the last three months (months 4, 5, and 6) of the double-blind treatment phase
- Achievement of 100% reduction from baseline in monthly migraine days at assessment timepoints
- Change from baseline in mean monthly acute headache medication treatment days over the last three months (months 4, 5, and 6) of the double-blind treatment phase
- Change from baseline in monthly acute headache medication treatment days at assessment timepoints
- Change from baseline in monthly acute migraine-specific medication treatment days at assessment timepoints
- Change from baseline in mean monthly hours of migraine headache over the last three months (months 4, 5, and 6) of the double-blind treatment phase
- Change from baseline in monthly hours of migraine headache at assessment timepoints
- Change from baseline in mean monthly average severity of migraine pain over the last three months (months 4, 5, and 6) of the double-blind treatment phase
- Change from baseline in monthly average severity of migraine pain at assessment timepoints
- Change from baseline in mean monthly migraine days with severe pain over the last three months (months 4, 5, and 6) of the double-blind treatment phase
- Change from baseline in monthly migraine days with severe pain at assessment timepoints
- Change from baseline in mean monthly hours of severe migraine pain over the last three months (months 4, 5, and 6) of the double-blind treatment phase
- Change from baseline in monthly hours of severe migraine pain at assessment timepoints
- Change from baseline in migraine pain interference with daily activities as measured by the migraine symptom interference items over the last three months (months 4, 5, and 6) of the double-blind treatment phase at assessment timepoints
- Change from baseline in the overall impact on everyday activities score as measured by the Migraine Physical Function stand-alone item items over the last three months (months 4, 5, and 6) of the double-blind treatment phase

- AMG 334 exposure and PK-PD relationships

10.1.1.4 Clinical Home Use Substudy

10.1.1.4.1 Primary Endpoint

- **Subject-reported outcome of attempted full-dose administration on day 29 and day 57**

10.1.1.4.2 Secondary Endpoint

- **Subject incidence of adverse events, serious adverse events, and adverse device effects**

10.1.1.5 Definitions of Terms Included in Endpoints

Migraine Day: Any calendar day in which the subject experiences a qualified migraine headache (onset, continuation, or recurrence of the migraine headache). A qualified migraine headache is defined as a migraine with or without aura, lasting for ≥ 30 minutes, and meeting at least one of the following criteria (a and/or b):

- a) ≥ 2 of the following pain features:
 - Unilateral
 - Throbbing
 - Moderate to severe
 - Exacerbated with exercise/physical activity
- b) ≥ 1 of the following associated symptoms:
 - Nausea and/or vomiting
 - Photophobia and phonophobia

If the subject took a migraine-specific medication (ie, triptan or ergotamine) during aura or to treat headache on a calendar day, then it will be counted as a migraine day regardless of the duration and pain features/associated symptoms.

Headache Day: Any calendar day in which the subject experiences a qualified headache (initial onset, continuation or recurrence of the headache). A qualified headache is defined as:

- a qualified migraine headache (including an aura-only event that is treated with acute migraine-specific medication), or
- a qualified non-migraine headache, which is a headache that lasts ≥ 30 minutes and is not a qualified migraine headache, or

- a headache of any duration for which acute headache treatment is administered.

Acute Headache Medication Treatment Day: Any calendar day during which the subject took an acute headache medication (migraine-specific or non-migraine-specific).

Acute Migraine-specific Medication Treatment Day: Any calendar day during which the subject took a migraine-specific medication (ie, triptan or ergotamine).

Monthly eDiary Data: Data collected by the eDiary in any 28-consecutive day interval relative to study day 1 when **at least** 14 days of eDiary data are collected within that 28-consecutive day interval. **Monthly frequency measurements will be prorated to 28-day equivalents.**

Migraine Attack: An episode of any qualified migraine headache. The following rules will be used to distinguish an attack of long duration from two attacks, or to distinguish between attacks and relapses:

- a) A migraine attack that is interrupted by sleep, or temporarily remits, and then recurs within 48 hours (ie, ≤ 48 hours between the start of the migraine attack to the time of the recurrence) will be considered as one attack and not two.
- b) An attack treated successfully with medication but with relapse within 48 hours (ie, ≤ 48 hours between the start of the migraine attack to the time of the recurrence) will be considered as one attack.

10.1.2 Analysis Sets

The full analysis set (FAS) includes all subjects who were randomized in the study. The efficacy analysis set includes subjects in the FAS and who received at least one dose of investigational product and **had** at least one **change from baseline measurement in** monthly migraine days **during** the double-blind treatment phase. In the efficacy analysis set, subjects will be analyzed according to randomized treatment, regardless of the treatment received. The per-protocol set is a subset of the efficacy analysis set that includes subjects who completed the 24-week double-blind treatment phase with no major protocol violations. For safety endpoints, all randomized subjects who received at least one dose of investigational product (ie, safety analysis set) will be analyzed **according to the randomized treatment unless a subject has received the incorrect dose during the entire double-blind treatment phase.** The open-label analysis set (OLAS) will consist of all subjects receiving at least one dose of AMG 334 in the **OLTP**. This analysis set will be used when summarizing data collected during the **OLTP**.

All subjects enrolled in the CHU substudy will be included in the CHU substudy analysis set.

10.1.3 Covariates and Subgroups

All analyses of efficacy endpoints will be adjusted for the effect of the stratification factor of prior/current treatment with migraine prophylactic medication (current migraine prophylactic medication treatment vs prior migraine prophylactic medication treatment only vs no prior or current migraine prophylactic medication treatment) and the baseline value. The primary, secondary efficacy, and selected safety endpoints will be analyzed in the subgroups defined by the stratification factor as well as **baseline monthly migraine days (< 8 days vs ≥ 8 days), prior prophylactic failure status (failed any vs not failed any), and BMI (< median vs ≥ median).**

10.2 Sample Size Considerations

The primary endpoint is the change from baseline in mean monthly migraine days over the last three months (months 4, 5, and 6) of the double-blind treatment phase. Using the treatment effect compared to placebo of -1.12 and -1.30 for the AMG 334 70 mg and 140 mg dose groups, respectively and a common standard deviation of 2.8 based on a Japan topiramate trial (www.clinicaltrials.gov), the planned sample size of 131 subjects in the placebo, 70 mg and 140 mg dose groups will provide 90% and 96% power for a two-sided test with significance level of 0.05 to show the superiority of AMG 334 70 mg and 140 mg compared to placebo, respectively. The proposed number of subjects in the 28 mg (n=66) dose group with the placebo (n=131), the 70 mg (n=131) and the 140 mg (n=131) dose groups is sufficient to demonstrate a dose-response using MCP-Mod analysis with the minimum power of 95% and provide the estimates of response in a Japanese population, using an assumed treatment effect of -0.55 for the AMG 334 28 mg dose group.

Clinical Home Use Substudy

Approximately 50 subjects will be enrolled in to the CHU substudy. The following assumptions are made based on the minimum sample size of 50 subjects: 5% of subjects per treatment group discontinue IP and 90% of the remaining subjects respond that they administered a full dose. As such, the anticipated distribution of responses per treatment group at a planned visit would be 5% categorized as not attempting due to discontinuing IP, 85.5% responding that they administered a full dose, and 9.5% responding that they did not administer a full dose. The associated 95% confidence interval halfwidths with 25 subjects per group are

8.5%, 13.8%, and 11.5%, respectively. The anticipated 95% confidence interval half width for the difference between treatment groups in the proportion of subjects administering a full dose is 19.5%. The discontinuation rate is expected to be less than 5% and the rate of administering a full dose is expected to be greater than 90%, and therefore these calculations are anticipated to be lower bounds. Calculations were performed using nQuery Advisor 7.0.

10.3 Access to Individual Subject Treatment Assignments by Amgen or Designees

Blinded individuals will not have access to unblinded information until the study is formally unblinded. Unblinding and potentially unblinding information should not be distributed to the study team, investigators or subjects prior to the study being formally unblinded (eg, the unblinding of investigators and subjects may occur at the final analysis rather than during the primary analysis) except as specified (eg, [Section 5.2](#) and [Section 9.2.2](#)).

Individual subject treatment assignments will be maintained by the IVR/IWR System. The independent Biostatistics group external to Amgen will have access to treatment assignments and will provide unblinded results, including aggregate and subject level data, to the DMC for data reviews for safety monitoring. Any unplanned unblinding occurring during the study period will be documented and reported in the final clinical study report.

Staff from Clinical Supply Chain, Biological Sample Management, PK and Drug Metabolism, Clinical Immunology, Department of Molecular Sciences & Computational Biology, and Global Biostatistics Sciences departments who are responsible for tracking, assaying, or analyzing biological samples or checking the accuracy of randomization during the conduct of this study are considered unblinded to the treatment assignments in this study. These individuals will not have access to subject level clinical data apart from the samples they are assaying and analyzing during the course of the study.

The analysis plan will detail the analyses and describe the timing for unblinding according to Amgen's standard operating procedure.

10.4 Planned Analyses

10.4.1 Data Monitoring Committee (DMC)

An independent DMC will review and make recommendations regarding the safety of the study participants throughout the double-blind treatment phase of the study, and until treatment assignment information is available to the study team for the primary analysis.

The DMC will be composed of external advisors, including at least 2 clinicians and a biostatistician. Summaries of data at the treatment group level will be prepared and presented by an independent biostatistician at the DMC meeting. Additionally the DMC will review pharmacokinetic data and compare the results against pre-defined criteria for observed and predicted data to potentially recommend discontinuation of enrollment into one or more of the AMG 334 treatment groups, in which case randomization of the remaining subjects would continue for the remaining treatment groups.

10.4.2 Interim Analysis

During the **OLTP** of the study, an interim analysis is planned after at least 100 subjects randomized to **140 mg** of AMG 334 have completed **26 and 52 weeks** of treatment with investigational product. The purpose of this interim analysis is to evaluate the long-term efficacy and safety of AMG 334 in subjects with episodic migraine after the 24-week double-blind treatment phase.

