Procedures: After signing informed consent, subjects will enter the screening phase. The screening phase is composed of an initial screening phase (up to 3 weeks) followed by a 4-week baseline phase. At the day 1 visit, eligible subjects will be enrolled (ie, randomized) into the 24-week double-blind treatment phase and will begin to receive double-blind investigational product QM SC. During the double-blind treatment phase, 3 SC injections are to be given for each investigational product administration (ie, at day 1 and weeks 4, 8, 12, 16, and 20) to maintain the dose-level blinding. At the week 24 visit, subjects will be entered into the 76-week **OLTP** and will begin to receive open-label AMG 334.

After IRB approval of Protocol Amendment 2, the 24-week double-blind treatment phase is followed by a 76-week OLTP with the dose determined by the subject's week 48 status:

- (1) **Subjects who have already completed the week 48 visit will continue to receive open-label AMG 334 70 mg QM SC (OL70) for a total of 76 weeks.**
- (2) **Subjects who have not yet completed the double-blind treatment phase and are not yet in the open-label phase will receive AMG 334 140 mg QM SC (OL140) upon entering the open-label phase and continue receiving open-label AMG 334 140 mg QM SC for 76 weeks.**
- (3) **Subjects who have not yet completed the week 48 visit but are in the open-label phase receiving AMG 334 70 mg QM SC must increase their dose to AMG 334 140 mg QM SC and continue receiving open-label AMG 334 140 mg QM SC until the week 100 visit (OL70-140) for a total open label phase duration of 76 weeks. The dose increase should be done at the first available opportunity, defined as the first**

visit after IRB approval of Protocol Amendment 2. Refer to [Table 3](#) for assessments to be collected at the visit of the dose increase and 12 weeks after the dose increase. At the time of the dose increase, the End of Open-label 70 mg electronic case report form (eCRF) page will need to be completed as subjects will be transitioning from 70 mg to 140 mg.

As a result of Protocol Amendment 2, there will be 3 possible dose sequences in the open-label phase, depending on completion of week 48 visit as noted above: (1) subjects receiving only AMG 334 70 mg QM SC in the open-label phase (OL70), (2) subjects receiving only AMG 334 140 mg QM SC in the open-label phase (OL140), and (3) subjects receiving both AMG 334 70 mg (for up to 24 weeks) and 140 mg QM SC (OL70-140).

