Refer to [Section 10.1.1.4](#) for the definition of migraine day. This definition of migraine day is consistent with the diagnostic criteria of migraine and probable migraine according to ICHD-3 and is consistent with those of the 20120178 Phase 2 episodic migraine trial. The mean monthly migraine days will be calculated using monthly migraine day data from the last 3 months (months 4, 5, and 6) of the double-blind treatment phase. A migraine day will be determined based on headache and medication information entered by subjects daily into a handheld electronic device (electronic diary; eDiary).

The secondary efficacy endpoints are the 50% responder rate and mean monthly migraine-specific medication treatment days. These secondary endpoints were selected because they are highly clinically relevant and provide complementary information to the primary endpoint in the evaluation of AMG 334 as a migraine prophylactic agent.

Rationale for AMG 334 Doses

Three dose levels of AMG 334 (ie, 28 mg, 70 mg, and 140 mg) were chosen for this Phase 2 study with the intent to bridge the data from the global Phase 3 episodic migraine study (20120296). These doses were selected in order to 1) demonstrate statistically significant improvement from placebo on the primary outcome measure, and 2) to establish the dose-response relationship of AMG 334 in Japanese subjects. **In the open-label phase, the dose of AMG 334 is being increased to 140 mg in a subset**

[figure not shown]
of subjects to provide continuous 1-year safety data for subjects receiving either AMG 334 70 mg or 140 mg.

The efficacy and safety of AMG 334 (7 mg, 21 mg, and 70 mg QM SC) were evaluated for the prevention of episodic migraine in a 12-week global Phase 2 study (20120178). The study randomized 483 subjects (AMG 334 7 mg [n=108], AMG 334 21 mg [n=108], AMG 334 70 mg [n=107] and placebo [n=160], QM SC) with a history of migraine for ≥ 12 months and a monthly migraine frequency of ≥ 4 and ≤ 14 migraine days.

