3. EXPERIMENTAL PLAN

3.1 Study Design

This is a Phase 2, multicenter, randomized, stratified, double-blind, placebo-controlled, parallel-group study of subjects with episodic migraine. The study is composed of an initial screening phase (up to 3 weeks), a 4-week baseline phase, a 24-week double-blind treatment phase, a 76-week OLTP, and a 12-week safety follow-up phase (16 weeks after the last dose of investigational product).

Approximately 459 eligible subjects will be randomized 2:1:2:2 to:

- Placebo (n ≈ 131)
- AMG 334 28 mg (n ≈ 66)
- AMG 334 70 mg (n ≈ 131)
- AMG 334 140 mg (n ≈ 131)

The randomization will be stratified by prior/current treatment with migraine prophylactic medication (current migraine prophylactic medication treatment vs prior migraine prophylactic medication treatment only vs no prior or current migraine prophylactic medication treatment).

Investigational product (ie, placebo or AMG 334) will be dosed QM, SC.

The overall study design is described by a [study schema](#) at the end of the Protocol Synopsis Section.

The study endpoints are defined in [Section 10.1.1](#).

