7.7 Interim Analysis Set

The Interim Analysis Set will include all subjects at the time when 100 subjects have completed 52 weeks of treatment with investigational product. The purpose of this interim analysis is to evaluate the long-term efficacy and safety of AMG 334 in subjects with episodic migraine after the 24-week DBTP.

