7.8 Subgroup Analyses

The primary and secondary efficacy will be analyzed in the subgroups defined by the stratification factor, BMI (< median vs \geq median), baseline monthly migraine days (< 8 vs \geq 8) and treatment failure of prior migraine prophylactic medications.

8. Interim Analysis and Early Stopping Guidelines

An independent Data Monitoring Committee (DMC) will review and make recommendations regarding the safety of the study participants throughout the DBTP of the study, and until treatment assignment information is available to the study team for the primary analysis. The DMC will be composed of external advisors, including at least 2 clinicians and a biostatistician. Summaries of data at the treatment group level will be prepared and presented by an independent biostatistician at the DMC meeting.

Additionally the DMC will review pharmacokinetic data and compare the results against pre-defined criteria for observed and predicted data to potentially recommend discontinuation of enrollment into one or more of the AMG 334 treatment groups, in which case randomization of the remaining subjects would continue for the remaining treatment groups.

During the OLTP of the study, an interim analysis is planned after at least 100 subjects randomized to 70 mg of AMG 334 have completed 52 weeks of treatment with investigational product. The purpose of this interim analysis is to evaluate the long-term efficacy and safety of AMG 334 in subjects with episodic migraine after the 24-week DBTP.

9. Data Screening and Acceptance

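### The interim trigger counts subjects randomised to 140 mg by total time on product, so it does not ensure the continuous 1-year exposure at 140 mg that Amendment 2 was meant to provide

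*Protocol*

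**What the plan says.** Protocol 10.4.2 sets the open-label interim: "an interim analysis is planned after at least 100 subjects randomized to 140 mg of AMG 334 have completed" a stated time, the time being given as subjects who "have completed 26 and 52 weeks of treatment with investigational product". No dose is attached to the 26 or 52 weeks. The section goes on: "The purpose of this interim analysis is to evaluate the long-term efficacy and safety of AMG 334 in subjects with episodic migraine".

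Protocol 6.2.1.1 (and the Synopsis, Procedures) assigns the open-label dose by where a subject stands when the IRB approves Amendment 2. Those past the Week 48 visit stay on 70 mg (OL70). Those still in the double-blind phase go to 140 mg at open-label entry (OL140). Those in open label but not past Week 48 move from 70 mg to 140 mg at the next visit (OL70-140), with up to 24 weeks at 70 mg. Randomised arm plays no part.

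Protocol 2.3 gives the reason for the change: the dose is raised in a subset "of subjects to provide continuous 1-year safety data for subjects receiving either AMG 334 70 mg or 140 mg".

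The SAP was written to Protocol 1.0, in which every subject received 70 mg open label. Its section 8 has "an interim analysis is planned after at least 100 subjects randomized to 70 mg of AMG 334 have completed 52 weeks of treatment", and its section 7.7 has "The Interim Analysis Set will include all subjects at the time when 100 subjects have completed 52 weeks of treatment with investigational product".

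**The concern.** In the design the SAP describes, a subject randomised to 70 mg who reached 52 weeks had spent them all at 70 mg, so counting by arm was the same as counting continuous exposure at one dose. The current trigger names the 140 mg arm instead, but a 140 mg-arm subject who entered open label before approval dropped to 70 mg at Week 24. That subject still counts in full. Subjects from the placebo, 28 mg and 70 mg arms who later complete an unbroken open-label year at 140 mg do not count towards the trigger at all.

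What is at stake is how the interim is timed and read. A row headed 140 mg could be taken as one year of 140 mg exposure when it mixes two doses.

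**Working it through.** **Inputs.** 459 subjects randomised 2:1:2:2, about 131 to 140 mg (Protocol 3.1). Double-blind doses on Day 1 and Weeks 4 to 20; open-label doses every 4 weeks from Week 24 to Week 96 (Protocol 6.2.1.1 and the dosing footnote to the Schedule of Assessments). The three open-label sequences are as above.

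**The plan's own figures.** 459 × 2/7 = 131.1, which matches. Open-label doses: (96 − 24)/4 + 1 = 19, and 19 × 4 = 76 weeks, which matches. An increase at Week 48 leaves Weeks 24 to 44 at 70 mg (6 × 4 = 24 weeks, matching the stated limit) and Weeks 48 to 96 at 140 mg (13 × 4 = 52 weeks). The dosing schedule itself therefore does allow a continuous year at 140 mg for every OL70-140 subject.

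**Exposure when a 140 mg-arm subject completes 52 weeks.** There are 6 double-blind doses and 7 open-label doses (Weeks 24 to 48), 13 in all. For an increase at Week w (28 to 48), the open-label 140 mg doses by Week 48 number (48 − w)/4 + 1, that is 6 down to 1.

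| Sequence | 140 mg doses of 13 | Longest unbroken time at 140 mg |
|---|---|---|
| OL140 | 13 | 52 weeks |
| OL70-140 | 7 to 12 | 24 weeks |
| OL70 | 6 | 24 weeks |

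For OL70-140 the second 140 mg run is at most 52 − 28 = 24 weeks, no longer than the double-blind run. The 26-week count has the same gap: 24 double-blind weeks plus one 4-week interval at 70 mg makes 28 weeks on product without 26 at 140 mg.

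**How many of the first 100.** Let k be the number of 140 mg-arm subjects already in open label at approval who go on to complete 52 weeks. If subjects reach 52 weeks in enrolment order, max(0, 100 − k) of the first 100 have an unbroken year at 140 mg: 100 for k = 0, 50 for k = 50, 10 for k = 90 and 0 for k ≥ 100. Zero therefore needs 100/131 = 76% of the arm in open label at approval with full retention. With an assumed 90% retention it needs 100/0.9, rounded up to 112, and 112/131 = 85.5%.

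**The zero case across the whole trial.** Assume one approval date and k ≥ 100. The 100th counted subject was then at Week 24 or later at approval, so the trigger falls within 52 − 24 = 28 weeks of it. OL70-140 subjects, and OL140 subjects from other arms, have at most 28 weeks at 140 mg by then. OL140 subjects from the 140 mg arm have fewer than 24 + 28 = 52. Nobody in any arm has the full year.

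**Illustration, with assumed accrual.** Take even accrual over 52 weeks and full retention. Subjects in open label at approval are those enrolled at least 24 weeks earlier.

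| Approval, weeks after first enrolment | 140 mg arm in open label | First 100 with an unbroken year |
|---|---|---|
| 40 | 40 | 60 |
| 60 | 91 | 9 |
| 76 | 131 | 0 |

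**When 52 continuous weeks at 140 mg are first reached.** 140 mg arm on OL140: Week 52. Other arms on OL140: 24 + 52 = Week 76. OL70-140: 28 + 52 = Week 80 to 48 + 52 = Week 100. OL70: never.

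**The case against.** The best defence is that the interim makes no dose-specific promise. Its stated purpose concerns AMG 334 in general; the 1-year aim in Protocol 2.3 explains the open-label dose change, not this trigger. No test or stopping rule is attached to the interim. SAP 7.7 admits all subjects to the Interim Analysis Set, so the arm count sets only the date. Later exposure is not lost, since the final analysis covers all study periods. SAP 10.6.7 already summarises exposure and dose changes, and a case report form page records the move from 70 mg to 140 mg. The SAP's 70 mg trigger is version lag, because it implements Protocol 1.0. All of this stands, and it limits the point to timing and reporting.

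It does not remove the point. Protocol 10.4.4 plans final open-label tables by double-blind group and overall, and SAP 10.5.3 tabulates open-label efficacy by randomised group. Neither plans a table by dose sequence, and SAP 10.6.7 does not give unbroken time at 140 mg.

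A reader might infer that the interim will be run with nobody at one year on 140 mg, or that most of the counted exposure was interrupted or at the other dose. The documents support neither. They give no accrual curve, approval dates or split by sequence, and each OL70-140 subject has at least 7 of 13 doses at 140 mg.

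**Conclusion.** The trigger in Protocol 10.4.2 does not measure the exposure that Protocol 2.3 sets out to provide. It can be met with anywhere from 0 to 100 of the first 100 subjects having an unbroken year at 140 mg. The zero end needs about 76% or more of the 140 mg arm in open label at approval, and more than that if some drop out. This rests on the wording of 10.4.2 and the sequences in 6.2.1.1; the counts also assume that subjects reach 52 weeks in enrolment order, and the trial-wide zero case assumes a single approval date. Approval dates that differ by site would blur the threshold without excluding zero. If most of the arm was still double-blind at approval, most of the 100 would have the full year.

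Neither type I error nor the primary analysis is touched. This is a point of definition and reporting that is cheap to settle.

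**What to change.** Reconcile Protocol 10.4.2 with sections 2.3 and 6.2.1.1 by stating whether the 26 and 52 weeks are counted by randomised arm or by dose received.

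If the present trigger is kept for its date:

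- report at the interim the number of subjects, from any arm, with at least 26 and at least 52 continuous weeks at 140 mg, and the same at 70 mg;
- define how a missed dose affects continuity, since Protocol 6.2.1.2 expects missed doses;
- summarise open-label safety and efficacy by sequence (OL70, OL70-140, OL140) as well as by randomised arm;
- do not describe the randomised-arm count as 1-year exposure at 140 mg.

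Update SAP 7.7 and 8 to match. The cost is a few extra tables from dosing data already collected.

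Changing the trigger itself to count exposure costs more. Apart from 140 mg-arm OL140 subjects, nobody qualifies before Week 76, and OL70-140 subjects qualify only between Weeks 80 and 100. The interim could move close to the final analysis, or never be reached if the OL70 group is large.
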